### 5.0 Specific aims

A. To determine the change in total sleep time as measured by polysomnography(PSG) in CLL patients with fatigue of  $\geq$  4(on a 0-10 scale) on the MD Anderson symptom inventory (MDASI) before and after the 1st cycle of treatment (day 57 +/- 3 days) with lenalidomide,

B.1. To summarize variables associated with sleep architecture as measured by PSG before and after the 1st cycle of treatment (57 days +/- 3 days) with lenalidomide, in this subset of population,

B.2. To summarize the variables associated with PSQI, Epworth sleep scale, actigraphy in relation to sleep and FACIT-F in relation to fatigue before and after treatment (57 days +/- 3 days) with lenalidomide.

B.3. To determine the relationship between changes in inflammatory cytokines levels and the frequency and intensity of fatigue and sleep disturbances in these patients as measured by the MDASI before and after the 1st cycle of treatment (57 days +/- 3 days) with lenalidomide.

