# 7.0 Patient Eligibility

### Inclusion criteria:

1.Patients to be 65 yrs or older.

2.Describe fatigue as being present every day for most of day for a minimum of 2 weeks and rate fatigue greater than or equal to 4 on a 0-10 scale, in which 0= no fatigue and 10=worst possible fatigue.

3. Have diagnoses of CLL and enrolled in a clinical trial of lenolidomide to treat CLL[A phase II study of lenalidomide as initial treatment of patients with chronic lymphocytic leukemia age 65 or older - 2006-0715, A Study of Lenalidomide in Patients with Chronic Lymphocytic Leukemia and Residual Disease after Chemotherapy -2007-0213]

4. Patients will be eligible to participate in this study if they rate sleep disturbance greater than or equal to 4 on a 0-10 scale, in which 0= disturbed sleep is not present and 10 = disturbed sleep as bad as you can imagine.

5. Have a MDAS of 13 or less.

6. Able to understand the description of the study and give written informed consent.

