## 8.0 Treatment Plan

Twelve eligible patients with CLL will be recruited from the Leukemia Clinic at MDACC. Patients complete questionnaires - MD Anderson symptom inventory(MDASI) for cancer related symptoms and screening for eligibility, Pittsburg Sleep Quality Index (PSQI), Epworth sedation scale, for assessment of sleep, FACIT-F to evaluate fatigue and quality of life and performance status is measured by Zubrod performance status and anxiety depression - Hospital anxiety depression scale(HADS). The laboratory correlates will include baseline hemoglobin level, electrolytes, serum IL-1, IL-6, IL-8 and TNF-á, IL-10 and MIP-1. This assessment will be performed a day before the initiation of therapy. Repeat assessments will be done on day 29 (+/- 3 days), and Day 57 (+/- 3 days), and again prior to the initiation of the next treatment phase. The day 15 (+/- 3 days) and day 43 (+/- 3 days) symptoms assessments will be performed via telephone. During the treatment period patient will wear an actigraph on the wrist to monitor physical activity. The actigraph will be used to record and evaluate sleep quantity and quality, daytime activity levels. Patient will maintain a sleep and fatigue dairy during the course of the treatment from prior to Day 1 to prior to the next treatment phase (at least 2 days). Patient will undergo polysomnography (PSG) to evaluate sleep pattern prior to Day 1 (after initial oncological visit) and prior to the next treatment phase (Day 57 (+/- 3 days)), at least 2 days prior to the initiation of treatment).

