e) **The Epworth sleep scale(ESS)**(Appendix H) is an 8-item questionnaire designed to asses general level of daytime sleepiness, and scores on this instrument range form 0-24, with higher scores indicating greater sleepiness.

Reliability has been tested for both scales and found to be good. A previous study determined within-subject reliability among 91 subjects who completed the PSQI on 2 occasions on average of 28 days apart. The Pearson correlation coefficient for the global score was 0.85(33). The Pearson coefficient in a trail involving 87 medical student over 5 months was 0.82.6 A study of the stability of both scores in 600 patients over one year was 0.68 and 0.76 for the PSQI and ESS respectively(34-36). The wide use of these validated instruments form the rational for using these scores to measure sleep quality and daytime sleepiness in our subjects(26-29).

f)**Sleep Diaries**: Sleep Diaries assess the following daily information: time of going to bed, final awakening, and arising from bed, sleep onset latency (SOL), numbers of awakenings (NWAK), wake after sleep onset (WASO), total sleep time (TSTS), sleep efficiency (SE), timing and duration of naps, and in the Pittsburgh Sleep Diary(PSD), sleep quality (30). Despite being subject reported they are widely used in research and in fact recommended I and considered essential in study of insomnia and other sleep disorders. The PSD has been used in numerous other sites to studies to evaluated sleep parameters(31).

g) **Actigraphy:** the measurement of physical movement using motion sensors reliably detects movements. As discussed in a major review and practice parameters (32), actigraphy provides an objective estimate of sleep and the 24-hour sleep wake rhythm and can detect circadian disturbances. Actigraphy can also be used to identify patients with sleep disorders who are overly active near bedtime or generally inactive throughout the day (33). Actigraphy will be measured from Day 0 to Day 57 (+/- 3 days).

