h) **Polysomnography** (PSG) is considered the "gold standard" for the objective measurement of sleep parameters. Recoding details are as follows. PSG is recommended or essential in the study of sleep disorders such as insomnia in determining Total sleep time, SOL, NWAK, WASO, SE, Apnea Hypopnea Index, PLMAI (Periodic Limb Movement Arousal Index), arousals and stages of sleep (sleep architecture)(30). PSG will be performed at the UT MDACC Sleep Center (directed by [name], co-Investigator) by a registered polysomnographic technologist. A sleep variable will be obtained using 12-channel polysomnography (Nihon Kohden, Foothills Ranch, CA). The twelve channels of data will include: central and occipital electroencephalogram, bilateral electrooculogram, submental electromyogram, thoracic and abdominal respiratory effort, airflow, electrocardiogram, tibialis electromyogram, and oximetry. Sleep record will be scored by registered polysomnographic technologists according to the standard criteria of Rechtschaffen and Kales. Records will be scored for total sleep time, number of minutes of wake after sleep onset (WASO), number of awakenings, sleep latency, sleep efficiency, and the percentages of stages 1,2,3,4, and REM sleep, as well as cortical arousals (defined as sudden increases in electroencephalogram frequency of at least 3 second duration, following at least 10 seconds of continuous sleep, with or without accompanying muscle activity). Study participation will involve 12 hours including arrival at the Sleep Center at approximately 8pm, completion of questionnaires, instrumentation with sensors, and completion of post sleep questionnaires. This assessment would be performed on prior to Day 1 and prior to the 2nd cycle (Day 57 (+/- 3 days)), at least 2 days prior to the initiation of treatment).

Laboratory evaluation: serum cytokines (IL-1, TNF-, IL-8, IL-10 and IL-6) at baseline before treatment, day 29 (+/- 3 days) and day 57 (+/- 3 days).

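### Aim B.2 compares actigraphy before and after treatment, but recording starts at an undefined Day 0, so the plan secures about one pre-treatment night or none (minor; cheap to improve)

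*Combined protocol and SAP*

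**What the plan says.** Aim B.2 (section 5.0) is to summarise, among other measures, "actigraphy in relation to sleep and FACIT-F in relation to fatigue before and after treatment". Two places give the recording window, and they differ:

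- Section 9.0(g): "Actigraphy will be measured from Day 0 to Day 57 (+/- 3 days" (the ±3 days appears to belong to Day 57, as it does at the other follow-up visits).
- Section 8.0: "During the treatment period patient will wear an actigraph on the wrist to monitor physical activity".

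Day 0 appears nowhere else in the text and is not defined. The other baseline measures are timed differently. For the questionnaires and laboratory tests, section 8.0 says "This assessment will be performed a day before the initiation of therapy". The first PSG is to "evaluate sleep pattern prior to Day 1 (after initial oncological visit", and section 9.0(h) agrees: "This assessment would be performed on prior to Day 1 and prior to the 2nd cycle". For the diary: "Patient will maintain a sleep and fatigue dairy during the course of the treatment from prior to Day 1".

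Section 10.0 lists actigraphy among the variables to be summarised. It does not say which nights make up the value before treatment and which the value after.

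**The concern.** A before-and-after summary needs a before value. The two descriptions of wear leave about one pre-treatment night or none, against some eight weeks of recording on treatment. The value of a wrist device is that it averages over many nights; a single baseline night gives that up on one side of the comparison. The analyst cannot repair this later, because nights not recorded before dosing are lost.

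There is also a problem of definition. With no averaging window stated, different before and after values can be built from the same record. Section 2.0 names actigraphy among the objective measures meant to give preliminary data for a larger randomised trial, so a usable estimate of change has some worth even in a pilot.

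**Working it through.** **The plan's own figure.** The only design calculation is the 0.89 SD detectable difference in section 10.0. A two-sided paired t test with n = 12, 11 df and alpha 0.05 has power 0.801 at 0.89 SD; the smallest difference with 80% power is 0.889 SD. The figure reproduces. It concerns PSG total sleep time and does not depend on actigraphy.

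**Counting nights.** Assume Day 1 is the first dose and Day 0 the day before. Pre-treatment nights = 1 − 0 = 1. Nights from Day 1 to Day 57 = 56 (53 to 59 with the ±3 days). If Day 0 is itself the dosing day, or section 8.0 is read literally, there are no pre-treatment nights.

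**An ambiguous phrase.** The PSG timing in sections 8.0 and 9.0(h) ends by requiring a gap of at least two days before treatment begins, with unbalanced brackets. Sections 9.0(b) and (c) attach similar words to the second cycle, so that is the likelier meaning. If the phrase also covers the first PSG, at least two pre-dose nights already exist on which the device could be worn.

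**What more nights would buy.** The documents give no variances, so every input here is assumed: night-to-night SD s within a patient; SD of true change t = 0.5s, 1s or 2s; b baseline nights; 7 end nights (my choice, not the plan's).

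SD of change = √(t² + s²[v(b) + v(7)]), where s²v(b) is the variance of a mean of b nights.

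- Independent nights: v(b) = 1/b.
- Correlated nights, AR(1) with ρ = 0.4, windows independent of each other: v(b) = (1/b)[1 + 2Σ(1 − k/b)ρᵏ], k = 1 to b − 1. This gives v(1) = 1, v(2) = 0.700, v(3) = 0.547, v(7) = 0.288.

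Example, independent nights, t = 0.5s: b = 1 gives √(0.25 + 1 + 0.143) = 1.180; b = 2 gives √(0.25 + 0.5 + 0.143) = 0.945; ratio 1.249.

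| Nights | t | SD, b=1 | b=2 | b=3 | b=7 | 1 vs 2 | 1 vs 3 | 1 vs 7 |
|---|---|---|---|---|---|---|---|---|
| Independent | 0.5s | 1.180 | 0.945 | 0.852 | 0.732 | 1.25 | 1.38 | 1.61 |
| Independent | 1s | 1.464 | 1.282 | 1.215 | 1.134 | 1.14 | 1.20 | 1.29 |
| Independent | 2s | 2.268 | 2.155 | 2.116 | 2.070 | 1.05 | 1.07 | 1.10 |
| AR(1) 0.4 | 0.5s | 1.240 | 1.113 | 1.042 | 0.909 | 1.11 | 1.19 | 1.36 |
| AR(1) 0.4 | 1s | 1.513 | 1.410 | 1.355 | 1.255 | 1.07 | 1.12 | 1.20 |
| AR(1) 0.4 | 2s | 2.300 | 2.233 | 2.199 | 2.139 | 1.03 | 1.05 | 1.07 |

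(SDs in units of s.)

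**As equivalent sample size.** With 12 patients the 95% CI half-width for mean change is 2.201/√12 = 0.635 times the SD of change. Solving t(0.975, n − 1)/√n × SD(b) = 0.635 × SD(1) for n gives the number of patients with b baseline nights who match 12 patients with one:

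| | b=2 | b=3 |
|---|---|---|
| Independent (t = 0.5s, 1s, 2s) | 8.6, 9.8, 11.1 | 7.5, 9.1, 10.8 |
| AR(1) 0.4 (t = 0.5s, 1s, 2s) | 10.2, 10.8, 11.5 | 9.2, 10.1, 11.2 |

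**The case against.** The strongest reply is that little is at stake. B.2 only summarises, in a 12-patient open-label pilot. A one-night baseline still yields a change, and on-treatment recordings remain usable. Pre-treatment sleep is also measured by PSG, by the PSQI over the preceding month, and by a diary that starts before Day 1 and records total sleep time, wake after sleep onset and sleep efficiency. All of this stands, and it is why the point is minor.

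The size rests wholly on assumed variances. The largest figure, 61%, needs seven baseline nights, independent nights and a true-change SD of only half the night-to-night SD, all together. With two or three correlated nights the gain is 3% to 19%. This also stands.

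More baseline nights may not be available. Therapy is given elsewhere: patients must be "enrolled in a clinical trial of lenolidomide to treat CLL", and those trials' schedules are not in these documents. Leaving PSG nights out altogether could remove the only baseline night for some patients. That stands too, and the fix below allows for it.

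What does not fall away is that the two sections disagree, Day 0 is undefined in the available text, and no nights are assigned to either value.

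**Conclusion.** The point holds as a cheap improvement to a secondary, descriptive aim. As written, the plan secures about one pre-treatment actigraphy night (assuming Day 1 is the first dose and Day 0 the day before) or none (section 8.0 read literally), and defines neither the before nor the after value. Under the stated assumptions, one baseline night makes the SD of change 3% to 25% larger than two nights, 5% to 38% larger than three and 7% to 61% larger than seven; the low ends are correlated nights and the high ends independent nights.

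Three stronger readings are tempting but not supported:

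- A reader might infer that there is no baseline and B.2 cannot be met. Section 9.0(g) starts at Day 0, which on the natural reading gives one night, and the two-day phrase in the PSG timing may mean that more nights are available.
- A reader might infer that the primary result is weakened. Total sleep time comes from PSG, and the 0.89 SD figure is untouched.
- A reader might infer a known loss of precision for the planned correlations. Any correlation using actigraphy change is also limited by a PSG change of one night against one night and by 12 patients, so no size can be assigned to the actigraphy baseline alone.

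**What to change.** 1. Define Day 0 and Day 1 relative to the first dose, and make sections 8.0 and 9.0(g) agree on when wear starts. Clarify whether the two-day phrase in sections 8.0 and 9.0(h) applies to the first PSG, the second, or both.
2. Issue the actigraph at the existing pre-Day-1 contact, when the diary starts, for wear on all available nights before Day 1. Do not delay therapy or exclude patients to gain nights.
3. State in section 10.0, in advance, that the before value is the mean of the available pre-Day-1 nights and the after value is the mean of a set number of nights before the Day 57 assessment (seven, for example).
4. Prefer home nights in both windows. Where the PSG night is the only pre-Day-1 night, keep it and flag it. Report the number and type of nights for each patient.

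The cost is protocol wording and a few more days of wearing a device already in use. The downside is that the number of baseline nights will vary between patients and may be small, so baselines will differ in precision; reporting the counts shows this but does not remove it.

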# **10.0 Statistics**

The primary objective is to explore a change in total sleep time using Polysomnography (PSG) in CLL patients with fatigue of greator or equal to 4 (in a 0-10 scale) on the MD Anderson symptom inventory (MDASI) before and after the 1st cycle of treatment (57days) with a Lenalidomide. We will use a paired t test, a Wilcoxon rank sum test, or a sign test (depending on the distribution of the data) to determine changes in total sleep time before and after treatment (day 57). Prior studies have indicated a clinically significant change in the total sleep time estimated by PSG to be 20 min, using a pilot open labeled design we anticipate obtaining a similar outcome by accruing 12 patients (34). Due to the challenge of accrual, expense and time constraints, a relatively small sample size has been selected. Assuming we will enroll 12 evaluable patients, we will be able to declare as significant differences between pre and post that are 0.89 standard deviations or greater with 80% power and a two-sided significance level of 0.05. We will summarize variables associated with sleep (PSG, Actigraphy, PSQI, ESS), fatigue (FACIT- F, HADS, actigraphy) and serum cytokines (IL-1, IL-6, IL-8 and TNF-á, IL-10 and MIP-1). In addition we will correlate these variables with changes in sleep time, using Pearson or Spearman correlation coefficients, depending on the distribution of the data. In addition this study will obtain preliminary data to determine the effect size for a future larger randomized controlledtrial.

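### Section 10 lists the Wilcoxon rank-sum test, which is for independent samples, as an option for the paired before/after comparison of total sleep time

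*Combined protocol and SAP*

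**What the plan says.** Section 10.0 (Statistics) gives the primary analysis in one sentence: "We will use a paired t test, a Wilcoxon rank sum test, or a sign test (depending on the distribution of the data"), to be used "to determine changes in total sleep time before and after treatment (day 57"). It states no rule for judging the distribution or for choosing between the second and third tests.

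The design is set out elsewhere. Section 5.0, aim A: "To determine the change in total sleep time as measured by polysomnography(PSG"). Section 8.0: "Twelve eligible patients with CLL will be recruited from the Leukemia Clinic at MDACC". Section 9.0, on polysomnography: "This assessment would be performed on prior to Day 1 and prior to the 2nd cycle". There is one group, each patient is measured twice, and there is no comparator.

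The power statement in Section 10.0, for 12 evaluable patients, concerns "differences between pre and post that are 0.89 standard deviations or greater with 80% power and a two-sided significance level of 0.05".

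**The concern.** The rank-sum (Mann-Whitney) test takes two independent samples. Here the two sets of values come from the same 12 people, so the test can be run only by treating the 12 baseline and 12 follow-up values as if they came from 24 different patients. Its null distribution is then wrong. With positive pre/post correlation, which is what one expects of a repeated sleep measure, it is usually conservative and loses power. With negative correlation it can exceed its nominal level.

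This sentence is the only specification of the primary test in the supplied text. An analyst who follows it literally could run an unpaired test on the primary endpoint. One who quietly substitutes the signed-rank test departs from the written plan. With 12 patients there is little power to spare.

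**Working it through.** **Inputs from the documents (Section 10.0):** n = 12 pairs, effect 0.89 SD, 80% power, two-sided alpha 0.05.

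**Inputs not in the documents, therefore assumed:** the pre/post correlation ρ (0.3, 0.5 and 0.7, with −0.3 and 0 as checks), the shape of the differences (normal or Laplace), and the rule that triggers the non-parametric test.

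**Step 1: reproduce the plan's figure.**
- Paired t-test: 11 df, critical value 2.201, noncentrality 0.89 × √12 = 3.083. Power is 80.1%, and the detectable effect at 80% power is 0.889 SD, so the stated 0.89 reproduces. Its unit is the SD of the within-patient differences.
- Two-sample t-test, 12 per group: 22 df, critical value 2.074, noncentrality 0.89 × √(12/2) = 2.180. Power is 55.0%, and the detectable effect is 1.20 SD.

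The plan was therefore powered as a paired comparison.

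**Step 2: what ignoring the pairing does.** With equal variances σ², the mean change has variance 2σ²(1 − ρ)/n. An unpaired test behaves as if it were 2σ²/n. Setting the SD of the differences to 1 gives σ = 1/√(2(1 − ρ)), so a shift of 0.89 becomes 0.89 × √(2(1 − ρ)) in units of σ: 1.05, 0.89 and 0.69 at ρ = 0.3, 0.5 and 0.7.

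**Step 3: exact two-sided rejection regions for n = 12.**
- Rank-sum: U ≤ 37 or ≥ 107, size 0.0449.
- Signed-rank: W ≤ 13 or ≥ 65, size 0.0425.
- Sign: ≤ 2 or ≥ 10, size 0.0386.

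**Step 4: worst case, rank-sum always used (simulated, normal data, equal variances, shift 0.89 SD of the differences).**

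| ρ | Rank-sum power | Rank-sum type I error |
|---|---|---|
| −0.3 | 87% | 7.4% |
| 0 | 80% | 4.4% |
| 0.3 | 67% | 2.0% |
| 0.5 | 52% | 0.9% |
| 0.7 | 27% | 0.2% |

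Whatever ρ is, paired t has 80% power, signed-rank about 76% and the sign test about 61%. If instead follow-up is a normal baseline plus an independent change, rank-sum power at ρ = 0.3, 0.5 and 0.7 is 72%, 60% and 33%.

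**Step 5: a more realistic reading.** Suppose paired t is used unless a Shapiro-Wilk test on the differences gives p < 0.05, and the non-parametric test is used then. That happens in about 5% of trials with normal differences and 17% with Laplace differences. Overall power at ρ = 0.3, 0.5 and 0.7 (20,000 simulated trials per setting):

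| Differences and model | Switch to rank-sum | Switch to signed-rank | Switch to sign |
|---|---|---|---|
| Normal, equal variances | 79.9, 78.7, 77.6% | 80.2, 79.8, 80.0% | 79.9, 79.4, 79.6% |
| Normal, baseline plus change | 79.9, 79.2, 77.8% | 79.8, 79.8, 79.7% | 79.5, 79.5, 79.3% |
| Laplace, equal variances | 80.2, 77.8, 73.6% | 82.0, 82.0, 81.8% | 83.1, 82.9, 83.0% |
| Laplace, baseline plus change | 84.0, 81.5, 74.8% | 82.0, 82.4, 81.5% | 83.2, 83.5, 82.6% |

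The largest loss against signed-rank is 81.8 − 73.6 = 8.2 points. The most favourable case for rank-sum is a gain of 84.0 − 82.0 = 2.0 points. Type I error with the switch to rank-sum is 3.6% to 5.4% over these settings.

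**The case against.** The strongest reply is that this is a naming error and not a wrong plan. The term stands between two tests that suit paired data, the sentence is about change within patients, there is no second group, and the 0.89 figure fits only a paired test. If the 12 changes are what is analysed, a rank-sum test cannot be run at all. Harm requires that the data look non-normal, that this option is preferred to the sign test, and that it is then applied literally. The study is an exploratory pilot, and neither its sample size nor the effect estimate it passes to a later trial depends on the name of the test.

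All of this stands, and it limits the weight of the point. Two further cautions also stand. The size of the effect rests on assumptions that the documents do not supply: the baseline-plus-change model at ρ = 0.3, for instance, implies a follow-up variance about 11 times that at baseline (1/0.3² = 11.1). And the 27% figure requires rank-sum to be used every time, which the plan does not say.

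What does not follow is that the text can be left alone. The sentence is the operative specification of the primary test, and the test it names does not fit the design.

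**Conclusion.** The concern holds, as a minor point. As written, Section 10.0 offers an independent-samples test for paired data, and no supplied text corrects it. It is most likely a slip for the signed-rank test.

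If rank-sum is reached only through a normality check, the effect on power relative to signed-rank runs from essentially none to about 2.5 points lost with normal differences, and from a 2-point gain to about an 8-point loss with Laplace differences. The steep losses in Step 4 apply only if rank-sum is always used. Type I error is not materially inflated for the non-negative correlations examined; at ρ = −0.3, always using rank-sum would give about 7.4%. All of these sizes depend on the assumed correlation, distribution and selection rule. The mismatch between test and design does not. The stated sample size and the 0.89 SD figure are unaffected.

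**What to change.** In Section 10.0, change the second listed test from the Wilcoxon rank-sum test to the Wilcoxon signed-rank test. This is a change of one term, with no extra patients, data or procedures and no change to the power statement.

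Two additions would be helpful but are not needed to correct the error: name the paired t-test as the primary test, since it is the one powered, and state that the 0.89 is in units of the SD of within-patient differences.

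### Section 10.0 lets the 12 observed differences choose among three primary tests with no rule or default, while its 80% power at 0.89 SD is the paired t test's figure

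*Combined protocol and SAP*

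**What the plan says.** Section 10.0 (Statistics) of the combined protocol and SAP lists the candidates for the primary test in one sentence: "We will use a paired t test, a Wilcoxon rank sum test, or a sign test (depending on the distribution of the data". The purpose is "to determine changes in total sleep time before and after treatment (day 57"). No check of distribution, threshold, order of preference or fallback is named there, and no other section settles the test.

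The same section then gives one power statement. It begins "Assuming we will enroll 12 evaluable patients" and claims to detect differences of "0.89 standard deviations or greater with 80% power and a two-sided significance level of 0.05". It does not say which of the three tests this describes.

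**The concern.** The choice is to be made from the same 12 differences that are then tested, by a criterion left to the analyst. Two things follow.

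- **The operating characteristics are undefined.** Power and type I error belong to a complete procedure, and here part of the procedure is missing. A figure that is right for one of the three tests is presented as if it held for the plan.
- **The hypothesis moves with the data.** The t test concerns the mean change, the signed-rank test a typical shift under symmetry, and the sign test whether more than half of the patients improve. With symmetric differences these coincide. With skewed differences they do not, and skew is what would steer the analyst away from the t test.

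At stake are the reading of the one primary p-value and whether a later reader can tell that the reported test was chosen for the shape of the data and not for its result.

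**Working it through.** **Inputs from Section 10.0:** n = 12 evaluable pairs; shift 0.89 SD; 80% power; two-sided α = 0.05. I take the SD to be that of the pre-post differences. The shapes of the differences and the selection gate below are assumptions, because the documents give none. For the rank test I use the signed-rank test, the version for paired data. That the plan names the rank sum test is a separate matter.

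**Step 1. Reproduce the stated figure.** For a paired t test, power = P(|T| > t₀.₉₇₅,₁₁), where T is noncentral t with 11 df and noncentrality 0.89 × √12 = 3.083. With critical value 2.201 the power is 0.801, and 80% is reached at 0.889 SD. The plan's figure reproduces. A normal approximation does not match (86.9% at 0.89 SD; 80% at 0.81 SD), nor does a one-sided t test (89.3%).

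**Step 2. Power at 0.89 SD if another test were fixed, normal differences.**
- Sign test: rejecting at 10 or more of 12 in either direction has size 2 × (66 + 12 + 1)/4096 = 0.0386. Lowering the limit to 9 would give 2 × (220 + 79)/4096 = 0.146, so 10 is needed. With p = Φ(0.89) = 0.813, power = 66p¹⁰(1−p)² + 12p¹¹(1−p) + p¹² = 0.606. Reaching 80% takes 1.12 SD.
- Signed-rank: reject when the smaller rank sum is 13 or less (exact size 0.0425). Simulated power is 0.760 (200,000 runs).

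These are powers of a test used in every sample. They are not the power of a choice that depends on the data.

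**Step 3. A data-driven choice.** Assumed gate: paired t test if Shapiro-Wilk p > 0.05; otherwise the sign test if |sample skewness| > 1, else signed-rank. Rejection rates with zero mean change, about 30,000 runs per shape for the gate:

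| Shape of differences | t test alone | Gate | Smallest of three p-values |
|---|---|---|---|
| Normal | 5.0% | 5.2–5.3% | 6.6% |
| t with 3 df | 4.1% | 4.9% | 6.5% |
| Laplace | 4.3% | 4.9% | 6.6% |
| Lognormal, log-SD 0.5 | about 7.6% | about 10% | about 12% |
| Exponential | 9.4% | about 15% | about 16% |

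Power at 0.89 SD, gate against t test alone: normal about 80% against 80%; Laplace 84% against 81%; t with 3 df 91% against 86%.

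**Step 4. Can 12 values guide the choice?** Shapiro-Wilk at 0.05 flags about 22% of t(3) samples, 31% of the lognormal samples and 54% of exponential samples. Most non-normal samples of moderate degree would therefore still go to the t test, and those diverted are a selected subset.

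**The case against.** The strongest reply is that this is a pilot. The objective is worded as exploratory: "The primary objective is to explore a change in total sleep time using Polysomnography (PSG"). The sample size is openly a matter of feasibility: "Due to the challenge of accrual, expense and time constraints, a relatively small sample size has been selected". No confirmatory decision rests on the p-value. That stands, and it limits the weight of the point. It does not make the power statement and the open choice of test consistent with each other.

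Three stronger readings are tempting, and the documents support none of them.

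- *The plan loses about 20 points of power if the sign test is chosen.* The 61% applies to a sign test used on every normal sample. The plan ties the choice to the distribution, and under the assumed gate only about 3.5% of normal samples reach the sign test, so overall power stays at about 80%. With heavy tails the alternatives can match or beat the t test: at 0.89 SD and 3 df, signed-rank 88%, sign test 86%, t test 86%.
- *A sign test would leave no result in minutes to set against the 20-minute benchmark.* A test supplies a p-value and does not prevent the change from being summarised. Section 10.0 separately plans summaries of the PSG variables and an effect size for a later trial.
- *The plan permits reporting the most favourable p-value.* It does not say so. The 6.6% for normal data is a worst case for unrestricted choice, outside the written plan.

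It is also fair to object that the t test is itself above 5% under skew. That is true, but in these simulations the gate is worse for the mean change.

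**Conclusion.** The point holds in limited form. The plan states a data-driven choice among three tests without a rule, and attaches to it a power figure that is the paired t test's. For symmetric differences the harm is small: size stays near 5%, and power is equal or higher under the assumed gate. The measurable cost appears with skewed changes of zero mean, where type I error for the mean rises from about 7.5–9.5% (t test alone) to about 10–15% (gate).

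This rests on the assumed gate and shapes; another rule would give other figures. It also counts as an error any rejection when the mean change is zero. Under skew the sign test has a different null hypothesis, so part of the excess reflects the change of question. I rate the point minor to moderate: worth correcting because the correction is cheap, but no threat to the pilot's purpose.

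**What to change.** Replace the sentence listing the three tests with wording such as: *The primary analysis is a two-sided paired t test, at the 0.05 level, on the change in PSG total sleep time from baseline to day 57, reported as mean change in minutes with a 95% confidence interval. The signed-rank test with its Hodges-Lehmann estimate (and, if wanted, the sign test) is a sensitivity analysis and does not replace the primary analysis, whatever the shape of the data.* Add that the 0.89 SD / 80% figure refers to the paired t test.

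The cost is one or two sentences, with no effect on patients, visits or budget. The downside is that the t test is only approximate at n = 12 under strong skew, as the table shows; reporting the sensitivity analyses alongside lets a reader see when this matters. A fully prespecified selection rule with its own simulated power and size would also close the gap, but it is more complex and depends on a weak check at this sample size.
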